2.9.2. Statistical Tests

An intent-to-treat analysis will be conducted. Selected baseline characteristics and outcome measures will be compared using the independent t test for continuous variables and the X^2 or Fisher's exact test for categorical variables as appropriate. Mann-Whitney U test will be used for non-parametric comparisons. Tests with a p-value < 0.05 will be considered significant.

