women with obesity (BMI ≥ 30 kg/m²). The exact mechanism of failed cervical ripening and dysfunctional labor patterns in obese women is not completely understood. Elevated cholesterol levels have been shown to decrease uterine contractility, and obese women are more likely to have elevated cholesterol levels than are normal-weight women¹⁶. In addition, obesity has been associated with lower prostaglandin sensitivity when used locally for cervical ripening⁸. This association is directly proportional to obesity class. Although many reviews list obesity as a risk factor for failed IOL, this risk has yet to be quantified by obesity class in relation to the various methods available for cervical ripening. In a large study of 1273 women who underwent IOL with vaginal misoprostol, obese women had a longer induction-to-delivery interval (median 22.7, 24.9 and 27.0 hours for normal weight, BMI between 30-39.9 kg/m² and BMI ≥ 40 kg/m², respectively; P < 0.01) and higher CD rates (21.3%, 29.8% and 36.5% for normal weight, BMI between 30-39.9 kg/m² and BMI ≥ 40 kg/m², respectively; aOR 2.32, 95% CI 1.58-3.42). These results were adjusted for parity, race and treatment group. Noteworthy, obese women were more likely to require a CD during the first stage of labor when compared to normal-weight women (74% and 83% vs 62%, respectively). These results were further confirmed by Wolfe et.al.⁹ in a large cohort of 80,887 women from the Ohio Department of Health's Birth Certificate Database. Indeed, pregnant women with class III obesity had a 2.89 aOR of failed IOL rates when compared to normal-weight women. These authors concur that more research is required to define the best method of cervical ripening that would decrease CD rates in this high risk populations.

The combination of Foley balloon plus vaginal misoprostol has not been prospectively compared to the use of vaginal misoprostol alone among women with BMI ≥ 30 kg/m². We hypothesize that obese pregnant women and unfavorable cervix (Bishop score ≤ 6), IOL ≥ 32 weeks gestation using the Foley balloon plus vaginal misoprostol will result in reduced cesarean delivery rates when compared to vaginal misoprostol alone. To prove this hypothesis, we propose a comparative-effectiveness, open-label, randomized controlled trial of induction of labor with transcervical foley balloon and vaginal misoprostol versus misoprostol alone for cervical ripening in obese pregnant women and a Bishop score ≤ 6 .

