2.1.5. Secondary Outcome Measures: Neonatal

- Neonatal intensive care unit (NICU) admission
- Transient tachypnea of the newborn (TTS)
- Respiratory distress syndrome (RDS)
- Meconium aspiration syndrome
- Culture proven sepsis
- Seizures
- Composite of adverse neonatal outcomes:
 - Apgar score ≤ 7 at 5 mins
 - Umbilical cord pH < 7.1
 - Neonatal injury: brachial plexus injury, fracture
 - Perinatal death

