2.7. Intervention and Procedures

[figure not shown]
Nulliparous pregnant women at ≥ 32 weeks' gestation admitted to labor and delivery for IOL and who meet the inclusion and exclusion criteria will be approached by the research staff (Figure 1). Group 1 will be composed of women allocated to the Foley balloon plus misoprostol. These women will receive vaginal misoprostol per standard protocol at 25 micrograms every 4 hours. In addition, a 26 Fr-Foley balloon catheter will be inserted by routine clinical standards. The Foley will be inserted through the internal cervical os, filled with 60 mL of normal saline, and then pulled snugly against the internal os. The catheter of the Foley will be taped to the patient's inner thigh under gentle traction. If the Foley is unable to be placed, the patient will be reexamined in 1 hour and placement will be reattempted if Bishop's score is still 6 or less by the healthcare provider. When the Foley balloon had fallen out or had to be removed because 12 hours have passed since insertion as per protocol, further management of labor will be left at the discretion of the labor team.

Group 2 will be composed of women allocated to vaginal misoprostol-only. These women will receive 25 micrograms of misoprostol per vagina every 4 hours. This time interval has been shown to be more effective than different time intervals in a Cochrane review²⁰. Once the cervix becomes favorable (Bishop score > 6), misoprostol administration will be discontinued. Similarly, further management will be left at the discretion of the labor team.

In both groups, if IV oxytocin is indicated, it will be withheld until 4 hours after the last dose of misoprostol to prevent uterine hyperstimulation. Other aspects of labor management will be similar for both groups, including continuous electronic fetal monitoring with external Doppler device or fetal scalp electrode. Uterine contraction assessment will be performed with either an external tocodynamometer or an intrauterine pressure catheter.

Participant data including demographic characteristics, medical and obstetric history, labor course and outcomes will be collected by a dedicated research nurse.

Figure 1. Flow Diagram – CROWN Trial

[figure not shown]

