2.9. Statistical Considerations

2.9.1. Sample Size

Assuming a cesarean delivery rate of 53% at Memorial Herman Hospital among nulliparous obese women who underwent IOL in 2012 at ≥ 32 weeks and met our inclusion criteria, 250 women (125 women per group) would be required for 80% power to detect a 33% cesarean delivery rate reduction between the 2 groups using a two-tailed t test and α of 0.05 (Table 2). Interim analysis after 50% enrollment will be performed in order to determine if the risk of adverse events discussed in the secondary outcomes is increased in one arm relative to the other arm.

Table 2. Proposed Sample Size

| % decrease in CD rate | Power (%) | | |
|-----------------------|-----------|-----|-----|
| | 80 | 85 | 90 |
| 33 | 250 | 270 | 316 |
| 40 | 172 | 196 | 228 |

| | | | |
|----|-----|-----|-----|
| 50 | 100 | 114 | 134 |
|----|-----|-----|-----|

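### Section 2.9.2 plans only crude tests, although gestational age, Bishop score and BMI are known at entry; the tests are valid, but pre-specified adjustment would gain some precision, mainly for NICU and respiratory outcomes

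*Combined protocol and SAP*

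**What the plan says.** Section 2.9.2 is the whole analysis plan. It sets an intent-to-treat analysis and then says "Selected baseline characteristics and outcome measures will be compared using the independent t test for continuous variables". The sentence goes on to chi-square or Fisher's exact tests for categorical variables, and that is the clause that governs cesarean delivery, NICU admission, transient tachypnea and RDS. Mann-Whitney is added for non-parametric comparisons. No regression model, covariate or adjusted estimate appears.

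Section 2.3 makes gestational age (32 weeks or more), Bishop score (6 or less) and BMI (30 or more) entry criteria. Section 2.6 stratifies randomization by center only. Section 2.7 adds that "Participant data including demographic characteristics, medical and obstetric history, labor course and outcomes will be collected by a dedicated research nurse". Section 2.1.5 lists NICU admission, transient tachypnea and RDS as separate secondary outcomes.

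**The concern.** The 32-week limit lets the trial mix moderately preterm and term births, and NICU admission and respiratory outcomes depend on maturity. Neither the randomization nor the analysis takes account of gestational age. These outcomes also inform the safety reading: section 2.9.1 plans an interim comparison of adverse events among the secondary outcomes at 50% enrollment, and section 2.8.2 leaves safety monitoring to the principal investigator and mentor.

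For cesarean delivery, Bishop score and BMI are plausible predictors, and the sample size leaves no spare power. Adjustment for either set of outcomes is most credible if it is fixed before outcomes are seen. If the arms happen to differ in preterm share, a model chosen afterwards will look driven by the data.

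**Working it through.** **The plan's own figure.** Section 2.9.1: "Assuming a cesarean delivery rate of 53% at Memorial Herman Hospital among nulliparous obese women", with "80% power to detect a 33% cesarean delivery rate reduction between the 2 groups", "using a two-tailed t test and α of 0.05". Read as a relative reduction, the treated rate is 0.53 × 0.67 = 0.355. The pooled two-proportion formula without continuity correction gives 126 per group, 252 in total, against the plan's statement that "250 women (125 women per group) would be required". Power at 125 per group is 79.9%. The figure reproduces.

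**Neonatal outcomes, using NICU admission.** The documents give none of these inputs, so they are assumptions: preterm share q of 5-25%; NICU rate a of 30-60% if preterm; NICU rate b of 8% if term.

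- Overall rate: p = qa + (1−q)b
- Share of variance explained by preterm status: R² = q(1−q)(a−b)² / [p(1−p)]
- Equivalent sample size: 250/(1−R²)
- Crude 95% half-width: 1.96 × √[2p(1−p)/125]
- Adjusted half-width: crude × √(1−R²)

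| q | a vs b | p | R² | Equivalent N | Crude half-width | Adjusted half-width |
|---|---|---|---|---|---|---|
| 5% | 30% vs 8% | 9.1% | 0.00230/0.0827 = 2.8% | 257 | 7.1 | 7.0 |
| 10% | 30% vs 8% | 10.2% | 0.00436/0.0916 = 4.8% | 262 | 7.5 | 7.3 |
| 5% | 60% vs 8% | 10.6% | 0.01284/0.0948 = 13.6% | 289 | 7.6 | 7.1 |
| 25% | 60% vs 8% | 21.0% | 0.0507/0.1659 = 30.6% | 360 | 10.1 | 8.4 |

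Half-widths are in percentage points. The calculation uses the same NICU rate in both arms and a preterm/term split in place of weeks.

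**Chance imbalance.** The SD of the between-arm difference in preterm share is √[2q(1−q)/125].

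- q = 10%: SD 3.79 points. A 1-SD imbalance shifts the NICU difference by 3.79 × 0.22 = 0.83 points, against a crude standard error of 3.83 points.
- q = 25%: SD 5.48 points. The shift is 5.48 × 0.52 = 2.85 points, against a crude standard error of 5.15 points.

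The squared ratios are (0.83/3.83)² = 0.047 and (2.85/5.15)² = 0.306, which match R² up to rounding. The shift is therefore a component of the crude standard error and does not add to it.

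**Cesarean delivery.** The Background gives 29.8% for BMI 30-39.9 and 36.5% for BMI 40 or more. With an assumed equal split, p = 33.15% and R² = 0.25 × 0.067² / (0.3315 × 0.6685) = 0.00112/0.2216 = 0.5%, worth about 0.2 points of power. The documents give no figure for Bishop score. With an assumed R² for Bishop score and BMI together, and effective n = 125/(1−R²) per arm:

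- R² 2%: power 80.7%
- R² 5%: power 81.9%
- R² 10%: power 83.9%

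Simulation of 6,000 trials of 250 women agrees. At R² of about 3%, power was 80.1% crude and 81.7% adjusted; at about 7%, 80.1% and 83.3%. Over all the scenarios simulated, type I error was 4.7-5.4% for both analyses.

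**The case against.** The strongest objection is that nothing here is an error. Unadjusted tests in a randomized trial are legitimate, and the plan may choose them. That stands. A reader might infer that entry from 32 weeks biases the neonatal comparison, or that chance imbalance in preterm births adds error that the confidence interval misses. The documents support neither: allocation is random, and the imbalance shift is already inside the crude standard error.

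The neonatal size rests wholly on assumed inputs. That also stands. The 360-woman equivalent needs 25% preterm and 60% NICU admission together; at 5% and 30% the gain is nearly nil.

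A reader might take the Background cohort as a precedent for adjustment, because it says "These results were adjusted for parity, race and treatment group". It is not one. That study compared BMI classes, which are not randomized, so its adjustment dealt with confounding. None of the three covariates at issue was among its adjustment factors, and parity is fixed in this trial by the nulliparous criterion.

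It is also tempting to call adjustment free. It is not quite. RDS and other outcomes may have few events, and a logistic model with arm, three centers and gestational age can become unstable or separate if those events cluster in a small preterm group. Finally, an adjusted cesarean analysis added without a stated hierarchy would leave the primary outcome with two p-values.

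What the objection does not remove is that the entry data are in hand, and that pre-specification is cheap now and hard to defend later.

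**Conclusion.** The point holds as an inexpensive gain in precision; it does not correct a bias. Every outcome in section 2.9.2 gets a crude test although three candidate covariates are known for every woman at entry.

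- **NICU admission:** gestational age explains about 3-31% of variance under 5-25% preterm and 30-60% vs 8% NICU rates. The 95% half-width falls from about 7.1 to 7.0 points at the low end and from 10.1 to 8.4 at the high end. All these inputs are assumed. Transient tachypnea and RDS follow the same reasoning but were not quantified.
- **Cesarean delivery:** the gain is modest, about 1-4 points of power for an assumed R² of 2-10%. The only figure that can be drawn from the documents, BMI class, gives about 0.2 points, so any larger gain must come from Bishop score or from BMI as a continuous variable.

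**What to change.** In section 2.9.2:

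1. For NICU admission, transient tachypnea and RDS, pre-specify logistic regression with arm, center and gestational age in weeks, standardized to a risk difference with a 95% confidence interval.
2. Fix in advance an event-count threshold below which the exact test is used instead. It should cover RDS as well as culture-proven sepsis and seizures.
3. For cesarean delivery, pre-specify one adjusted analysis with arm, center, Bishop score and continuous BMI, standardized in the same way. State in advance whether it or the chi-square test is primary, and report the other as a sensitivity analysis.

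The cost is plan wording. The entry values are established at eligibility, so no new data are needed. The remaining downside is model instability with sparse events, which step 2 limits.

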2.1.4. Secondary Outcome Measures: Maternal

- Indication for CD
- Induction-to-delivery interval (hours)
- Need for oxytocin augmentation
- Occurrence of tachysystole (≥ 5 contractions in a 10 minute period averaged over a 30-minute window) requiring terbutaline or Pitocin cessation.
- Clinical chorioamnionitis: maternal fever $\geq 100.4\text{F}$, uterine fundal tenderness, maternal or fetal tachycardia ($>100/\text{min}$ and $>160/\text{min}$, respectively) and purulent or foul amniotic fluid¹⁹
- Need for operative vaginal delivery
- Composite of maternal morbidity:
 - Maternal ICU admission
 - Postpartum endometritis
 - Surgical-site infections prior to discharge
 - Venous thromboembolism
 - Need for transfusion
 - Maternal death

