2.5. Recruitment and Feasibility

Recruitment will occur at the Labor and Delivery units at Memorial-Hermann Hospital – Texas Medical Center, Lyndon B. Johnson General Hospital and Kern Medical, Bakersfield, CA.

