2.6. Randomization

Randomization will be achieved by computer-generated random sequences. Permuted block randomization will be performed, stratified by center. Women will be randomized to either Foley balloon plus misoprostol or misoprostol alone as the method of choice for IOL. Enrollment number and assignments will be placed in opaque sealed envelopes. Envelopes will be kept secured in a locked office and will be accessible only by the research personnel.

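### Randomization is stratified by center but no planned test uses center, so the primary test is slightly conservative if cesarean rates differ between hospitals

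*Combined protocol and SAP*

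**What the plan says.** Section 2.6 (Randomization) states: "Permuted block randomization will be performed, stratified by center". Section 2.5 begins "Recruitment will occur at the Labor and Delivery units at" and goes on to name three hospitals, so there are three strata.

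Section 2.9.2 (Statistical Tests) is the only section that names analyses. Its main provision reads: "outcome measures will be compared using the independent t test for continuous variables and the X^2", with Fisher's exact test as the alternative for categorical data. It adds: "Mann-Whitney U test will be used for non-parametric comparisons". None of these tests uses center, and no other section adds a stratified test, a center covariate or a regression model.

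The only cesarean rate used for planning comes from one hospital (section 2.9.1): "Assuming a cesarean delivery rate of 53% at Memorial Herman Hospital among nulliparous obese women". No rates or enrollment shares are given for the other two.

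**The concern.** Permuted blocks within center keep the arms almost equal in size at every hospital. A hospital with a high cesarean rate then contributes equally to both arms, and its high rate cancels out of the arm difference. The pooled chi-square test ignores this. It estimates variance as if all women came from one population, so variation between hospitals stays in its standard error. When center rates differ, that standard error is too large, the true type I error falls below 5%, and some power is given up.

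Differences between hospitals are plausible. Section 2.7 says that once the balloon is out, "further management of labor will be left at the discretion of the labor team", and cesarean delivery is itself a management decision. That says nothing about how large the differences are.

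What is at stake is efficiency, not validity. The design has little slack: 125 women per group gives almost exactly 80% power.

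**Working it through.** **Inputs from the documents.** Control cesarean rate 53%, reduction 33%, 125 women per group, two-sided α 0.05 (section 2.9.1); three centers (2.5); blocking within center (2.6). The 33% must be a relative reduction, giving 0.53 × 0.67 = 0.3551; an absolute 33-point reduction would need only 66 women in total.

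**Assumptions.** The rates and sizes of the centers, exact 1:1 balance within center, and the same relative risk at each center.

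**1. The plan's own sample size.** With p̄ = (0.53 + 0.3551)/2 = 0.44255,

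n = [1.96·√(2·0.44255·0.55745) + 0.8416·√(0.53·0.47 + 0.3551·0.6449)]² / 0.1749² = (1.3767 + 0.5819)² / 0.03059 ≈ 125.4, rounded up to 126 per group, 252 in total.

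The stated 250 agrees closely. The same approximation gives 79.9% power at 125 per group.

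**2. Excess standard error under the null.** The pooled variance per woman is 0.53 × 0.47 = 0.2491. With three equal centers at 53% + d, 53% and 53% − d, the between-center variance is 2d²/3. Under blocking, the true variance is 0.2491 − 2d²/3. The ratio of the standard error used to the true one is r = √[0.2491/(0.2491 − 2d²/3)], and the approximate true type I error is 2·[1 − Φ(1.96·r)].

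- d = 0.10: 2d²/3 = 0.0067, r = 1.014, type I error 4.7%
- d = 0.15: 2d²/3 = 0.0150, r = 1.031, type I error 4.3%
- d = 0.20: 2d²/3 = 0.0267, r = 1.058, type I error 3.8%

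**3. Simulation.** Pooled chi-square versus Cochran-Mantel-Haenszel (CMH), both without continuity correction, with 41 or 42 women per arm at each center. There were 200,000 to 400,000 trials per scenario, so the Monte Carlo standard error of a power figure is at most √(0.8·0.2/200,000) ≈ 0.09 points.

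| Spread of center rates | Type I error, pooled | Type I error, CMH | Power, pooled | Power, CMH |
|---|---|---|---|---|
| none | 4.93% | 4.93% | 79.6% | 79.6% |
| ±5 points | 4.84% | 4.85% | 79.6% | 79.7% |
| ±10 points | 4.62% | 4.75% | 79.8% | 80.1% |
| ±15 points | 4.25% | 4.94% | 80.1% | 81.4% |
| ±20 points | 3.75% | 5.05% | 80.5% | 83.2% |

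At ±5 the gain is under 0.1 point before rounding.

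**4. Unequal centers.** With a 60/25/15% split (75, 31 and 19 women per arm), rates recentered to a weighted mean of 53%, and all six placements of the high, middle and low rate:

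- ±10 points: gain of 0.1 to 0.4 power points; pooled type I error 4.6% to 4.8%
- ±20 points: gain of 1.4 to 3.0 power points; pooled type I error 3.7% to 4.3%

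Across all scenarios CMH keeps the type I error between 4.7% and 5.2%.

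**5. Rare outcomes.** At an assumed event rate of 1%, 2.5 events are expected in 250 women. The chance that at least one of three equal centers has none is 1 − (1 − 0.99^83.3)³ = 82%. At 2% it is 46%. A stratified test is unattractive there. Fewer than 10 events in total means an expected count below 5 per arm, which is a natural point to keep Fisher's exact test.

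**The case against.** The best case for leaving the plan alone is that nothing valid is at risk. The planned test's power does not fall as hospitals diverge; in equal centers it rises slightly, from 79.6% to 80.5%. The loss exists only relative to a better test. Up to a 20-point range between hospitals (±10) the gain is at most 0.4 points, and nothing in the documents supports the 40-point range needed for 2 to 3 points. At ±10, part of the shortfall from 5% is discreteness: CMH itself runs at 4.75%, against 4.62% for the pooled test. All figures assume exact balance within center and a constant relative risk; no block size is given, and incomplete blocks would shrink the effect a little. The gains were also computed only for the primary outcome.

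All of this is correct as to size, and it rules out any claim that the trial is underpowered or its error rate uncontrolled. It does not remove the mismatch between randomization and analysis. The stratified test loses essentially nothing when center rates are equal, gains when they differ, and needs nothing the trial does not already collect. Adopting center adjustment only after the outcomes are known would look data-driven, so it should be settled in advance.

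**Conclusion.** The concern holds, as a small, conditional and costless improvement. The trial stratifies by center and plans no analysis that uses center. If cesarean rates differ between hospitals, the primary test is conservative: under the assumed equal-center scenarios its type I error is about 4.6% at ±10 points and 3.8% at ±20. The power forgone is nil with equal rates, 0.1 to 0.4 points at ±10 over both center splits, and 1.4 to 3.0 points at ±20, which should be read as an extreme case. The center rates and shares are assumptions throughout. Type I error is not inflated, and the planned 80% power is not missed on this account.

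**What to change.** Amend section 2.9.2 along these lines:

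- **Primary outcome.** Compare cesarean rates with a Cochran-Mantel-Haenszel test stratified by center. Report the center-stratified (Mantel-Haenszel) risk difference and relative risk with 95% confidence intervals. Keep the unstratified chi-square test as a sensitivity analysis.
- **Continuous secondary outcomes.** Use a linear model with arm and center as factors. Where Mann-Whitney would have been used, use the center-stratified van Elteren test.
- **Binary secondary outcomes.** Use the Cochran-Mantel-Haenszel test, except that outcomes with fewer than 10 events in both arms together keep the unstratified Fisher's exact test. This covers rare events such as "Maternal death" (section 2.1.4) and "Perinatal death" (section 2.1.5), if tabulated separately from their composites.
- **Indication for cesarean.** If analyzed as several categories, it can keep the planned chi-square or Fisher's exact test.

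The cost is a few sentences in the statistical section. Sample size, data collection and conduct are unchanged. The primary outcome is the priority; the secondary changes are for consistency with the design.
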